### **2.2 Secondary Objective:**

- Assess safety and tolerability of metformin treatment in subjects undergoing external beam radiation treatment for head and neck cancer.

- To determine the effect of metformin treatment on symptoms of **xerostomia** as assessed by the Xerostomia Questionnaire (XQ)
- To determine the effect of metformin treatment on symptoms of **mucositis** as assessed by WHO classification
- To determine the effect of metformin treatment on symptoms of **dysphagia** as assessed by the MD Anderson Dysphagia Inventory
- To determine the effect of metformin treatment on symptoms of **Fatigue** as assessed by the Multidimensional fatigue inventory (MFI).

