### **6.1 Study Visit Schedule**

Screening: Trial Coordinator will screen the office charts for possible inclusion in the trial. Labs for the screening part will be available from pre-admission testing that is standard of care.

Visit 1: Subjects that meet the inclusion criteria after reviewing the initial biopsy, laboratory data and clinical chart will be approached the day of their follow up after initial biopsy. The study coordinator will meet with the prospective candidates and go over the protocol, answer questions and obtain informed consent. If the subject is agreeable to the study, a physical exam will be performed, blood and saliva will be collected, and participant will be randomized.

Metformin/placebo Instructions on how to take study drug will be given and times for follow up phone calls for tolerability and safety will be arranged with participants. Participants will be instructed to call with any side effects or adverse events that occur in the interim of the follow up phone calls. The exact date to start the metformin will be determined this visit based on the planned start of radiation. Subject will be instructed to start taking the metformin/placebo at any point from 1 to 7 days from the start of radiation.

Quality of life measures including the EORTC QLQ – H&N35, mucositis score, Multidimensional fatigue inventory and the Xerostomia Questionnaire (XQ) will be administered on an iPad through the website ([https://az1.qualtrics.com/jfe6/preview/SV\\_87y9lyJ0sFo8oJv](https://az1.qualtrics.com/jfe6/preview/SV_87y9lyJ0sFo8oJv)). Patients will be identified only by an ID number.

Visit 2: Subjects will come in during the 3rd week of their radiation for blood draw, saliva collection, physical exam, quality of life questionnaires and tolerability assessment. An inventory of medication will also be taken to assess compliance. Location of radiation is not dictated by this protocol.

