Visit 3: Two weeks after completion of radiation. Subjects will be approached for bottle and pill reconciliation as well as follow up of side effects and adverse events. Blood and saliva will be collected, and MD Anderson Dysphagia Inventory, Multidimensional fatigue inventory (MFI-20) and the Xerostomia Questionnaire (XQ) will be administered will be administered on an iPad through the website ([https://az1.qualtrics.com/jfe6/preview/SV\\_87y9lyJ0sFo8oJv](https://az1.qualtrics.com/jfe6/preview/SV_87y9lyJ0sFo8oJv)). Patients will be identified only by an ID number.

Follow-up: Every 3 months during the 1st year post treatment subjects will have their regularly schedule appointments at which we will draw blood and saliva and administer quality of life surveys. The participant's medical records will be reviewed every 3 months for 12 months.

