## **Appendix A: Schedule of Events**

## Appendix A: Schedule of Events

| Study Procedures   | Screening | Visit 1 | Visit 2 (During 3 rd week of RT) | End of Treatment (Visit 3) E | Follow-up F |
|--|-----------|---------|---|---|------------------------|
| Informed consent   |           | X       |   |   |                        |
| Inclusion/Exclusion Criteria                                     | X         | X       |   |   |                        |
| Demographics, Medical history                                    | X         | X       |   |   |                        |
| Physical examination, vitals, weight, blood pressure             |           | X       | X   |   |                        |
| Randomization  |           | X       |   |   |                        |
| Quality of Life Questionnaires D                      |           | X       | X   | X                                       | X C         |
| Pathology Report histologic confirmation of disease if available | X         |         |   |   |                        |
| Concomitant meds   | X         | X       |   |   |                        |
| Toxicity and AE Assessment                                       |           | X       | X   | X                                       | X                      |
| Treatment/ Intervention                                   |           |         |   |   |                        |
| Metformin G   |           | X       | X   |   |                        |
| Placebo H   |           | X       | X   |   |                        |

|                                       |  |   |   |   |                |
|---------------------------------------|--|---|---|---|----------------|
| Radiation Treatment                   |  | X | X |   |                |
| Correlative Studies            |  |   |   |   |                |
| Blood sample collection A  |  | X | X | X | X C |
| Saliva sample collection B |  | X | X | X | X C |

- A. A Two 7ml purple top tubes are to be drawn at each time point and transported directly to [name] laboratory.
- B. B 5ml of saliva is to be collected at each time point and transported directly to [name] laboratory.

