- C. C Blood samples, saliva samples, and quality of life questionnaires will be collected every 3 months for the first year post treatment. Collection will occur at participant's regularly scheduled appointments.
- D. D Quality of life surveys include: EORTC QLQ – H&N35, mucositis score, Multidimensional fatigue inventory and the Xerostomia Questionnaire (XQ). All questionnaires will be administered online via an iPad provided at the visit.
- E. E Visit will be 2 weeks after the completion of radiation therapy.
- F. F Patients will be seen at regularly scheduled appointments every 3 months for the 1st year post treatment. Participant's medical records will be reviewed every 3 months for 12 months
- G. G The initial starting dose of metformin will be 500mg orally daily for 3 (+2 days) days which then will be increased to 500mg twice daily and, if tolerated, further increased to 1000mg twice daily after day 6 (+2 days). Patients will maintain 1000mg twice daily dosing until 2 weeks after completion of radiation. If patient must have CT scan with intravenous contrast, metformin will be held and participant will be instructed to start metformin the day following the scan.
- H. H Placebo will be given as 500mg tablets twice daily with no dose escalation

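### No visit in either schedule names all four secondary instruments of section 2.2, no baseline dysphagia inventory is named, and the planned objective response rate has no endpoint, definition or assessment

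*Combined protocol and SAP*

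**What the plan says.** Section 2.2 gives each symptom objective its own instrument. Xerostomia is measured by XQ and fatigue by MFI. Dysphagia is to be judged "as assessed by the MD Anderson Dysphagia Inventory" (MDADI below), and mucositis "as assessed by WHO classification". Section 2.4 lists the same four symptoms as secondary endpoints, without instruments.

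The visits are described twice.

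- **Section 6.1.** At Visit 1: "Quality of life measures including the EORTC QLQ – H&N35, mucositis score, Multidimensional fatigue inventory and the Xerostomia Questionnaire (XQ) will be administered". At Visit 3, two weeks after radiation ends: "MD Anderson Dysphagia Inventory, Multidimensional fatigue inventory (MFI-20) and the Xerostomia Questionnaire (XQ) will be administered". For Visit 2 and the three-monthly follow-up it refers only to quality of life instruments in general.
- **Appendix A.** Section 6.0 points to this as the schedule of events. It marks questionnaires at Visits 1, 2, 3 and follow-up, and footnote D defines the set once: "Quality of life surveys include: EORTC QLQ – H&N35, mucositis score, Multidimensional fatigue inventory and the Xerostomia Questionnaire (XQ".

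Sections 1.1 and 1.4 also list the secondary measures. Both include the EORTC H&N35 module, and neither includes MDADI.

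Section 7.2 summarises swallowing function and mucositis scores by arm. It then adds an objective response rate by arm with an exact 95% interval. The Study Summary has the same item.

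**The concern.** A questionnaire or mucositis score that is not taken at its visit cannot be reconstructed later, so the visit lists decide what the secondary analysis can contain. Dysphagia and mucositis are two of the four secondary endpoints. They are also the only two symptom outcomes that 7.2 names for summary, and they are the two on which the lists disagree.

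Without MDADI before radiation, a by-arm summary at Visit 3 cannot show whether the arms already differed on that scale, and no change on it can be described. If Appendix A is followed, there is no MDADI summary at all.

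The response rate is a separate matter. An interval is promised for a quantity that the trial does not define and does not plan to measure.

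**Working it through.** The plan gives no sample size, power or precision figure for the secondary outcomes, so there is nothing numerical to reproduce. The check sets the lists side by side.

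**Step 1. Instruments by visit.** Inputs: section 2.2, section 6.1, and Appendix A with footnote D. Each cell gives 6.1 first, then Appendix A.

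| Instrument | Visit 1 | Visit 2 | Visit 3 | Follow-up |
|---|---|---|---|---|
| XQ | named / named | general / named | named / named | general / named |
| MFI | named / named | general / named | named / named | general / named |
| Mucositis score | named / named | general / named | **not named** / named | general / named |
| MDADI | **not named** / **not named** | general / **not named** | named / **not named** | general / **not named** |
| H&N35 (not in 2.2) | named / named | general / named | not named / named | general / named |

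If the mucositis score is counted as the WHO classification, 6.1 names 3 of the 4 instruments at Visit 1 and 3 of 4 at Visit 3. Appendix A names 3 of 4 at every questionnaire visit. No visit reaches 4 of 4. Neither schedule says that the mucositis score is the WHO classification. Without that equation, Visit 1 of 6.1 and every visit of Appendix A fall to 2 of 4.

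**Step 2. The two Visit 3 lists.** Section 6.1 has 3 instruments and Appendix A has 4. They share 2 (MFI, XQ). That leaves 3 − 2 = 1 only in 6.1 (MDADI) and 4 − 2 = 2 only in Appendix A (H&N35, mucositis score).

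**Step 3. Which instruments have a named Visit 1 to Visit 3 pair?**

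- Following 6.1 alone: XQ and MFI. Mucositis has Visit 1 only, and MDADI has Visit 3 only.
- Following Appendix A alone: XQ, MFI, mucositis score and H&N35. MDADI is never given.
- Following both together: XQ, MFI, mucositis score and H&N35. MDADI still has Visit 3 only.

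The mucositis gap therefore depends on the reading. The missing MDADI baseline appears under all three.

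**Step 4. What 7.2 will summarise.** Section 7.2 does not say which instrument supplies swallowing function. Section 2.2 points to MDADI, while section 1.1 points to H&N35 among its measures.

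**Step 5. The objective response rate.** It is absent from the objectives and endpoints in sections 2.0 to 2.5. No response criteria or time point is given, and there is no evaluable set beyond the general rule in 7.3. Neither 6.1 nor Appendix A schedules a tumour assessment. Section 1.6 says the trial is not built to test efficacy against the cancer, and section 3.1 admits patients treated by surgery before radiation.

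**The case against.** Much can be said for the plan.

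- **Pooled over visits, 6.1 does name all four instruments**: the mucositis score, MFI and XQ at Visit 1, and MDADI at Visit 3. This is correct. A reader might infer that 6.1 leaves one out altogether, but the point holds only visit by visit.
- **Appendix A already schedules the mucositis score at Visit 3**, and a team that reads both texts together would collect it. This also stands. A reader might infer that the score will be lost at Visit 3. The documents show a conflict, not a certain loss.
- **The lists may not be exhaustive.** The wording at Visit 1 and in footnote D is open-ended, and Visits 1 and 3 give the same survey link, so one common battery may be intended. That is possible, but no text says so. The Visit 3 list has no open-ended wording, and footnote D, the only definition of the survey set, leaves MDADI out.
- **Dysphagia is not wholly without a baseline.** Section 1.1 counts H&N35 among the dysphagia measures, and it is given at Visit 1. It is a partial baseline on a different instrument, and 6.1 does not name it again at Visit 3.
- **The symptoms are seen elsewhere**, through "Toxicity and AE Assessment" in Appendix A and the three-monthly record review in section 3.1. Neither names MDADI or the WHO classification.
- **The secondary analysis is mainly descriptive.** This limits the weight of the point but does not remove it, because a descriptive summary also needs the data.

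For the response rate there is little defence. Section 4.5 seeks survival and progression for subjects who withdraw, but that does not supply a response assessment.

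**Conclusion.** The point stands as a conflict in the schedules and is worth correcting. No visit names all four instruments of 2.2. MDADI is named at one visit under 6.1 and at none under Appendix A, and at no baseline under either. The Visit 3 lists agree on 2 instruments and differ on 3. The objective response rate has no endpoint, definition or scheduled assessment. These statements rest on the text alone and need no numerical assumption.

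Three stronger inferences are not supported.

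- It cannot be said that patients already enrolled lack an MDADI baseline, because the content of the shared survey is not shown.
- It cannot be said how much precision is lost. Section 7.2 plans no test or baseline-adjusted comparison of these scores, and the documents give no correlation from which to work it out.
- It cannot be said that the trial's main result is at risk. The primary cytokine analysis does not use these lists.

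**What to change.** 1. Write one instrument-by-visit list and use it in sections 1.1, 1.4, 2.2 and 6.1 and in footnote D. Add MDADI at Visit 1. Keep both MDADI and the mucositis score at Visit 3, and state that the mucositis score is the WHO classification. Say whether H&N35 is a secondary instrument. MDADI at Visit 2 and follow-up is the sponsor's choice, but the list should state it.
2. In 7.2, name the instrument that supplies swallowing function.
3. Delete the objective response rate from the Study Summary and 7.2.

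The cost is brief extra questionnaire time at Visit 1 on the iPad already in use (the documents give no duration), plus wording changes. If the WHO score needs an examination, Visit 3 must allow for one, because Appendix A marks "Physical examination, vitals, weight, blood pressure" only at Visits 1 and 2. Patients already enrolled may lack an MDADI baseline if the shared survey did not include it. That should be checked against the survey itself and reported.

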## **6.2 Definition of Dose-Limiting Toxicities and early stopping rules:**

Toxicity will be evaluated using the most recent version (version 4) of the NCI toxicity criteria, i.e. the NCI Common Terminology Criteria for Adverse Events (CTCAE) version 4.0. The CTCAE provides descriptive terminology and a grading scale for each adverse event listed. A copy of the CTCAE can be found at <http://ctep.cancer.gov>.

Grade 4 toxicity (probably or definitely drug related): Treatment will be permanently discontinued.

## **6.3 Dose Delays and Dose Modifications**

Toxicity will be evaluated using the most recent version (version 4) of the NCI toxicity criteria, i.e. the NCI Common Terminology Criteria for Adverse Events (CTCAE) version 4.0. The CTCAE provides descriptive terminology and a grading scale for each adverse event listed. A copy of the CTCAE can be found at <http://ctep.cancer.gov>.

Grade 1 toxicity: Patient will be maintained on full dose.

Grade 2 toxicity: Dose will be reduced by 50% until grade 1 or lower. If symptoms are not resolved within 3 days of toxicity development the treatment will be interrupted definitively.

Grade 3 toxicity (probably or definitely drug related): Treatment will be interrupted. Toxicity will be evaluated daily and if toxicity improves to grade 1 or lower dose will be reduced by 50%. If toxicity is not improved or resolved or reduced to grade 1, treatment will be interrupted definitively.

Grade 4 toxicity (probably or definitely drug related): Treatment will be permanently discontinued.

In case of grade 1 or 2 diarrhea (the most frequent side effect) a concomitant administration of loperamide will be provided.

## **6.4 Laboratory Procedures/Evaluations**

### 6.4.1 Clinical Laboratory Evaluations

To assess changes in cytokines and exosomes, patients will have two 7ml purple top tubes drawn in the office as well as collection of 5ml of saliva. To assess the effects of metformin on serum and salivary exosome profiles, samples will be collected in person by office nursing staff at follow-up visits to the Department of Otolaryngology and transported directly to [name] lab.

### 6.4.2 Special Assays or Procedures

Exosome profiles of serum and saliva samples will be isolated and analyzed in the laboratories of Drs. [name] and [name] using previously established protocols.

### 6.4.3 Specimen Preparation, Handling, and Storage

Blood and saliva will be collected in the Department of Otolaryngology, de-identified and analyzed in the labs of [name] and [name].

## **7.0 STATISTICAL PLAN**

### **7.1 Analysis for Primary Outcome**

Mixed effects linear regression will be used to model longitudinal measurements of each cytokine. Measurement time will be treated as a categorical variable and fixed effects in the model will include randomization assignment, time, and randomization by time interaction. A linear contrast will be used to estimate the difference in randomization groups with respect to mean change from baseline to

post-treatment. Significance of this difference will be calculated for each cytokine and p-values will be adjusted using the Benjamini and Hochberg procedure to control the false discovery rate at 5%. Cytokine levels will likely need to be log-transformed prior to analysis to meet model assumptions.

Longitudinal measurements of exosomes will also be modeled using mixed effects linear regression in the same fashion. This analysis is treated as separate from the cytokine questions and the p-value will not be adjusted.

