| 
Statistical Methodology
 | 
The primary objective of the study is to assess the impact of metformin on cytokine and exosome profiles. All subjects from whom blood and saliva samples are obtained both pre-, during and post-treatment will be included in the primary analyses. Change in cytokine profiles will be evaluated using mixed effects linear regression.
 
Analysis of secondary outcomes will be primarily descriptive. The distribution of swallowing function and mucositis scores will be summarized. The objective response rate will be estimated along with an exact 95% binomial confidence interval.
   |
| 
Schema
                  | 
50 HNSCC patient candidates for adjuvant or neoadjuvant radiation
  <pre> graph TD     A[50 HNSCC patient candidates for adjuvant or neoadjuvant radiation] --> B[Pre-metformin blood and saliva samples]     B --> C[Randomized Metformin Treatment* (n=25) vs Placebo** Treatment (n=25)]     C --> D[external beam radiation (sample collected halfway through)]     D --> E[Post-metformin blood and saliva sample]   </pre> 
*Metformin (500 mg/day for 3 (+ 2 days) days followed by 500 mg twice daily for 3 days followed by 1000mg twice daily from day 6 (+2 days). Subjects will maintain 1000 mg twice a day dosing until two weeks post radiation. )
 
** Placebo (1 tab taken BID) No ramp up phase
 |

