### **2.1 Primary Objective:**

We have chosen a cytokine/chemokine profile analysis as a surrogate marker of trending inflammatory reaction. This response drives the severity of mucositis/xerostomia and acute radiation toxicity. The blood and saliva counts will be compared in the pre-treatment sample, during treatment samples and post treatment samples. Luminex technology with 40 cytokines markers will be used (Luminex technology with the Milliplex MAP Human Cytokine/chemokine Magnetic kit I (41 analytes) (sCD40L, EGF, Eotaxin, FGF-2, Flt-3 ligand, Fractalkine, G-CSF, GM-CSF, GRO, IFN- $\alpha$ 2, IFN- $\gamma$ , IL-1 $\alpha$ , IL-1 $\beta$ , IL-1ra, IL-2, IL-3, IL-4, IL-5, IL-6, IL-7, IL-8, IL-9, IL-10, IL-12 (p40), IL-12 (p70), IL-13, IL-15, IL-17A, IP-10, MCP-1, MCP-3, MDC (CCL22), MIP-1 $\alpha$ , MIP-1 $\beta$ , PDGF-AA, PDGF-AB/BB, RANTES, TGF- $\alpha$ , TNF- $\alpha$ , TNF- $\beta$ , VEGF). Blood and saliva samples will be drawn before, during and immediately after treatment and every three months thereafter for one year. All blood samples will be taken by a phlebotomist who will be blinded as to whether the patient is in the experimental (radiation + metformin) or control (radiation + placebo) groups.

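### Section 7.1 estimates a separate baseline mean per arm although baseline samples precede randomisation; a common-baseline model would usually be more precise (13–34% less variance at equal SDs, assumed correlation 0.7–0.3, complete data)

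*Combined protocol and SAP*

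**What the plan says.** Section 7.1 specifies the primary analysis: "Mixed effects linear regression will be used to model longitudinal measurements of each cytokine". The "fixed effects in the model will include randomization assignment, time, and randomization by time interaction", with time categorical. The test is a contrast: "A linear contrast will be used to estimate the difference in randomization groups with respect to mean change from baseline" to post-treatment. Exosomes are modelled in the same way. On scale, the section says only: "Cytokine levels will likely need to be log-transformed prior to analysis to meet model assumptions". It names no covariance structure or random effects and places no constraint on the baseline means.

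The baseline sample comes before allocation in two places. The schema in the Study Summary puts a box for "Pre-metformin blood and saliva samples" above the randomisation box. Section 6.1, Visit 1, gives the order: "blood and saliva will be collected, and participant will be randomized". Section 5.4 says only that allocation happens at accrual, but the sample in any case precedes study drug.

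Section 7.4 plans 25 participants per arm. It gives 80% power at 0.81 SD for exosomes and, with 5 of 40 cytokines truly different, at 1.1 SD for each cytokine. It does not say whether these are SDs of the change or of the level.

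**The concern.** Because the model includes an arm main effect, each arm has its own baseline mean, and the contrast subtracts the observed baseline difference in full. That fixes the slope of post-treatment on baseline at 1. Randomisation makes the expected baseline difference zero, so a model with one shared baseline mean can estimate the slope instead and so reduce the variance.

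Precision is scarce here: there are 25 per arm and a Benjamini-Hochberg correction over 40 cytokines. By the table in 7.4, the chance of detecting all five truly different cytokines is 0.33.

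How much is gained depends on the SD ratio as well as the correlation. Unequal SDs are plausible, because section 2.1 chose the profile "as a surrogate marker of trending inflammatory reaction" and log transformation is not yet settled. The covariance structure also matters, since a common baseline is safe only if the covariance is adequately modelled.

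**Working it through.** **The plan's own figures.** With 25 per arm, two-sided alpha 0.05 and a noncentral t on 48 df, 80% power is reached at 0.809 SD, which matches the stated 0.81. For five true differences, the single-test alpha is 0.8 × 5 × 0.05 / (35 × 0.95) = 0.0060, the detectable difference is 1.06 SD, and 0.8^5 = 0.33. These match 7.4.

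**Variance.** Let the baseline SD be 1, the post-treatment SD r and the correlation ρ. Neither ρ nor r is in the documents; ρ of 0.3, 0.5, 0.7 and r of 0.75 to 1.5 are assumptions. Up to the common factor 2/25:

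- planned change contrast: 1 + r² − 2ρr
- common-baseline model, large sample: r²(1 − ρ²)
- difference: (1 − ρr)², which is zero only at ρr = 1 and never negative

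Estimating the slope with 50 participants multiplies the second variance by 47/46. At r = 1, the ratio of the two variances becomes (1 + ρ)/2 × 47/46. For ρ = 0.5 that is 0.750 × 1.0217 = 0.766, so 23% is saved.

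Variance saved (complete data, slope estimated) and simulated power at 0.81 SDs of change, where the planned contrast has 80%:

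| Post/baseline SD ratio | Saved, ρ = 0.3 / 0.5 / 0.7 | Power, ρ = 0.3 / 0.5 / 0.7 |
|---|---|---|
| 0.75 | 53% / 47% / 43% | 98% / 97% / 96% |
| 1.00 | 34% / 23% / 13% | 93% / 89% / 85% |
| 1.25 | 20% / 9% / 0% | 88% / 84% / 80% |
| 1.50 | 11% / 1.5% / −2% | 84% / 80% / 79% |

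At equal SDs, the planned contrast would need 25/0.664 = 38, 25/0.766 = 33 or 25/0.868 = 29 per arm to match. At ρ = 0.9 the saving is only 2.9%, and at 0.95 it is 0.4%.

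**Validity of the alternative.** The recommended model (REML, unstructured, Kenward-Roger; baseline, week 3 and Visit 3) was simulated with 10,000 runs for each of the 12 combinations. Type I error was 4.8–5.3%, against 4.7–5.2% for the planned contrast with the same covariance. The variance ratios agreed with the formula (0.651, 0.765 and 0.868 at equal SDs), and every run converged.

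**Missing data.** Suppose 20% miss Visit 3 only and SDs are equal. In large samples the variance per arm is (1 − ρ²)/20 for the common-baseline model. The planned contrast has (1 − ρ²)/20 + (1 − ρ)²/25. The savings are 30%, 21% and 12%. With small-sample fits and losses reaching 20% by Visit 3, simulation gave 26%, 21% and 9%.

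**Random intercept only.** With two visits, this model assumes a common variance (1 + r²)/2. The true variance of the common-baseline estimate then exceeds the model's by the factor 2r²/(1 + r²), whatever ρ is. At r = 1.5 the factor is 4.5/3.25 = 1.385, and 1.96/√1.385 = 1.67 gives a type I error of 9.6%. At r = 1.25 it is 7.6%. With three visits, simulated error was 6.4–6.7% at r = 1.25 and 7.5–8.4% at r = 1.5. The planned contrast is also affected under this covariance: 6.4–6.8% at r = 0.75.

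**The case against.** The strongest objection is that nothing is wrong: the contrast is valid and pre-specified, the 7.4 figures reproduce, and choosing between two valid estimators in a pilot is a preference. That stands as a description, and the point is offered only as an efficiency gain. It remains worth making because the gain needs no new data.

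The size is also conditional. The range of 13–34% needs an assumed correlation, equal SDs and complete data. If inflammation widens the spread after radiation, the gain shrinks or disappears. The largest gain, 18 points of power, needs less spread after treatment than before. All of this stands. On the other side, the worst loss in the range examined is about 1 point of power.

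The baseline of 80% power assumes that 0.81 is in SDs of change. If it is in SDs of the level, at equal SDs, planned power is 66%, 80% or 95%, and the alternative gives 83%, 89% or 97%. The gain is 17, 9 or 2 points.

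The random-intercept results do not count against the plan, which names no covariance. They show why the structure must be specified with the common baseline.

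The testing has limits. The seven-visit model was simulated in one setting only (equal SDs, ρ = 0.5, 15 per arm by the last visit; 1,125 runs, all converged, type I error 5.3%). Skewed data were not simulated, and error was checked at 5% but not at alphas as small as 0.006. The fallback could also leave different analytes fitted with different models.

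Finally, the Study Summary limits the primary analysis to participants sampled before, during and after treatment, whereas 7.3 includes everyone with any data. Under the narrower population, the missing-data results would not apply.

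**Conclusion.** The point holds. Section 7.1 gives a valid analysis but spends information on a baseline difference that randomisation makes zero in expectation. Across assumed correlations of 0.3–0.7 and SD ratios of 0.75–1.5 with complete data, a common-baseline model with unstructured covariance changes the variance by between a 53% reduction and a 2% increase. Power at 0.81 SDs of change moves by between +18 and about −1 points. At equal SDs the saving is equivalent to 4 to 13 extra participants per arm. The gain is likely but not assured, because the two quantities that determine it are not in the documents.

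**What to change.** In 7.1, for cytokines and exosomes:

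- Keep baseline as an outcome record, with categorical time and arm-by-time terms for the post-baseline visits only. Drop the arm main effect, so that both arms share one baseline mean.
- Specify an unstructured within-participant covariance, REML and Kenward-Roger degrees of freedom. Do not use a random intercept alone.
- State in advance that, if the seven-visit fit (28 covariance parameters) does not converge for an analyte, the same model is fitted to baseline, week 3 and Visit 3 only (6 parameters). Using the three-visit model throughout would keep one model for all analytes.

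Everyone with any data stays in the analysis, as 7.3 requires. Two optional clarifications: say in 7.1 that post-treatment means the visit in 6.1 described as "Visit 3: Two weeks after completion of radiation", and say in 7.4 which SD the effect sizes use.

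The cost is two sentences and the matching model code, before data are analysed, with no new samples, visits or participants. The variance penalty was at most about 2% in the complete-data cases and 2.5% in the missing-data cases simulated.
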